2 STUDY OBJECTIVES AND ENDPOINTS

2.1 Study Objectives

2.1.1 Primary Objectives

- To assess the safety of two doses (12.5 mg and 25.0 mg DXA) of Dexamethasone acetate microspheres for extended-release injectable micro-suspension, SX600 (IMP) administered by transforaminal epidural injection to the lumbosacral epidural space at the L4- L5, L5-S1 level, or the S1 nerve root, compared to Placebo (0.9% Sodium Chloride Injection, BP), in the treatment of radicular pain resulting from inflammatory changes in a single affected nerve root secondary to lumbar disc herniation
- To assess the efficacy of two doses (12.5 mg and 25.0 mg DXA) of Dexamethasone acetate microspheres for extended-release injectable micro-suspension, SX600 (IMP) compared to Placebo (0.9% Sodium Chloride for Injection, BP), to alleviate the radicular pain from a single nerve root involvement secondary to lumbar disc herniation.
- To measure the systemic pharmacokinetics of two doses (12.5 mg and 25.0 mg) of Dexamethasone acetate microspheres for extended-release injectable micro-suspension, SX600 (IMP) from a single transforaminal epidural placement of 1.0 mL

2.1.2 Secondary Objectives

- To assess changes at 30-day intervals in functional outcomes following treatment
- To assess Patient Global Impression of Change
- To assess any decrease in the use of other health services
- To assess the time to loss of response in the Responders

2.2 Study Endpoints

2.2.1 Safety Endpoints

The Safety outcome will be assessed by:

Sponsor: SpineThera Australia Pty. Ltd

Protocol Number: CLIN-0012-STA01-19

SAP Version and Date: Amendment Final 1.1, 13JUL2022

- Adverse events from treatment day through study conclusion.
- Serious adverse events (SAEs) considered product or procedure-related.
- Neurological consequences of the transforaminal epidural injection (TF-EI).
- Non-laboratory adverse events following TF-EI.
- Laboratory adverse events following administration of IMP/Placebo.

Safety endpoints are as follows:

- Incidence of treatment-emergent AEs and SAEs grouped by body system.
- Changes from Baseline in clinical laboratory, urinalysis, vital signs, and ECG parameters to discharge and follow-up
- Changes from pre-dose physical exam findings to Follow-Up

2.2.2 Primary Efficacy Endpoint

- The proportion of 50% Responders at 60 days post-dosing, where a 50% Responder is defined as a patient with 50% or greater improvement from baseline in mean Worst Daily Leg Pain.

2.2.3 Secondary Efficacy Endpoints

- The proportion of patients who are 50% Responders (defined as having 50% or greater improvement in Mean Worst Daily Leg Pain score compared to baseline) at each of the other scheduled time points (14, 30, 90, 120, 150, and 180 days) post-dosing.
- Change in functional outcomes as measured by Patient's Global Impression of Change, Oswestry Disability Index and SF-36 QoL questionnaire at each visit.
- The proportion of patients who are 30% Responders (defined as having 30% or greater improvement in Mean Worst Daily Leg Pain) at each of the other scheduled time points (14, 30, 60, 90, 120, 150, and 180 days) post-dosing.
- Time to loss of response, in the subset of patients who are 50% Responders at Day 14 (50% or greater improvement in Mean Worst Daily Leg Pain).

2.2.4 Pharmacokinetic Parameters

- The maximum observed plasma concentration (C_{max}), time to C_{max} (T_{max}).
- The area under the plasma concentration versus time curve from time 0 (predose) to time infinity (AUC_{inf}).
- AUC from time 0 to time of last measurable plasma concentration (AUC_{last}).
- The percentage of the AUC that is extrapolated beyond the last measurable concentration (AUC_{ext}).
- The elimination rate constant (λ_z).
- The apparent systemic clearance (CL/F).
- Mean residence time (MRT).
- Apparent volume of distribution.
- Terminal phase (V_z/F), and terminal-phase half-life ($t_{1/2}$)

3 STUDY DESIGN

3.1 Study Design and Population

This first-in-human study is a Phase I/II, double-blind, parallel-group, randomized, placebo-controlled multi-centre trial. The study was originally designed to include 180 patients randomized 1:1:1 to receive the IMP (Dexamethasone acetate microspheres for extended-release injectable micro-suspension, SX600 at 12.5 mg or 25.0 mg) or Placebo (0.9% Sodium Chloride for Injection, BP) via transforaminal epidural injection to the lumbosacral epidural space at the L4- L5, L5-S1 level, or the S1 nerve root, as an outpatient procedure. The targeted patient total was decreased from 180 to 120 on 12 May 2021, which was documented in each sites Investigator Site File. The enrollment was stopped at 55 treated participants due to slow enrollment and the impact of Covid-19.

Patients will be screened to ensure they meet all inclusion and none of the exclusion criteria. Patients are considered enrolled in the study upon signing the Informed Consent Form by both the subjects and a study investigator (who is also a clinician). Informed Consent must be obtained prior to performing any study-related procedures. Section 21 of the protocol provides a complete list of inclusion and exclusion criteria.

Each patient will be followed for 180 days for assessment of any treatment-emergent adverse effects, status of radicular pain, functional assessments, and the use of health care services. Safety will be assessed through physical examination, vital signs, laboratory tests, and assessments of adverse events (AEs).

The study was originally expected to enroll over a period of 9 months. Each patient was expected to be in the study for 7 months. The total duration of the study was expected to be 19 months (9 months enrollment + 7 months follow-up + 3 months reporting). The 55 enrolled participants were enrolled over a two and a half year period and will be followed for the originally defined 180 days.

Systemic pharmacokinetics of dexamethasone (active moiety) were planned to be evaluated in a subset of approximately 60 patients (across IMP and placebo groups). By the time when the study is terminated by the sponsor, only 4 pharmacokinetic sub-study participants were enrolled.

3.2 Randomization and Blinding

Following the original plan in the protocol, patients who are eligible for enrollment into the study will be evaluated for randomization eligibility at Study Visits 1 and 2. The Biostatistician will prepare the randomization schedule, which will be managed by PCI Melbourne. Patients will be randomly assigned in a 1:1:1 ratio to one of two doses of SX600 (12.5 mg for the low-dose group, or 25.0 mg for the high dose group,) or Placebo (0.9% Sodium Chloride for Injection, BP or equivalent), with a planned final assignment of 60 patients/group. The list of randomized treatment assignments will be prepared by statisticians assigned to the study. The randomization number will be collected in the Electronic Data Capture (EDC) System. Refer to the Randomization Materials Specification Form for further details of randomization.

At the site, the physician who performs the TF-EI will be unblinded to the treatment assignment, but a second physician and study staff who are responsible for all subsequent patient assessments

Sponsor: SpineThera Australia Pty. Ltd

Protocol Number: CLIN-0012-STA01-19

SAP Version and Date: Amendment Final 1.1, 13JUL2022

must remain blinded to the treatment assignment. Since the reconstituted active IMP produces an opaque white suspension, it is not possible to blind the injector with a matching placebo solution for epidural administration, and hence 0.9% Sodium Chloride for Injection, BP has been chosen for the placebo comparator.

3.3 Sample Size Considerations

Limited data are available in the literature on which to base sample size/power considerations. In the study conducted by Ghahreman (Ghahremen, 2010) ⁽¹⁾, the primary endpoint was the proportion of patients who achieved a 50% or greater reduction from baseline at 30 days. In the steroid arm, the observed response rate was 54%. In the control arms of this study, the response rates were 7%, 13%, 19%, and 21%. Based on these results, the assumed true response rates are 50% (active) and 20% (placebo). Using a two-sided comparison of binomial proportions at the alpha=0.05 level of significance, a sample size of 60 patients per arm will provide 94% power. If the true active arm response rate is 50% and the true placebo response rate is 25%, then the power of the study is decreased to 81%.

Due to enrollment difficulties and the impact of Covid-19, the study is being terminated with a total sample size of 55 randomized patients. As a result, the originally planned efficacy analyses will not be conducted. Instead, the results of the study will be evaluated descriptively.

3.4 Safety Review Committee

A Safety Review Committee (SRC) will be assigned the responsibility of safety of the participants and will provide medical oversight and expertise to the Sponsor and sites concerning the continuation, modification, or termination of the trial. The SRC will monitor patient safety through pre-defined, periodic review of the clinical study safety data as well as relevant background knowledge about the disease, test agent/device, or participant population under investigation.

The SRC will provide safety oversight of the study per the National Health and Medical Research Council (NHMRC) Guidance on Data Safety Monitoring Boards 2018. The SRC will be composed of three to four members including a Clinical Research Organization (CRO) independent medical monitor, a biostatistician, one Investigational Site clinician and the Sponsor Chief Medical Officer. The study is double-blinded but the SRC can request unblinding to make determinations regarding study outcome.

Details of the SRC, including committee member names and responsibilities, timing of the SRC reviews, data to be reviewed, and halting criteria will be documented separately in the SRC Charter.

3.5 Interim Analysis

There are no interim analyses planned for this study.

3.6 Timing of Analyses

The final analysis will occur when the last patient completes the end-of-study visit. A topline analysis of the Worst Daily Leg Pain will be assessed at the time that the last enrolled patient completes their 90 day visit prior to full database lock. This top line analysis will include the analyses on the primary endpoint time of 60 days and a secondary endpoint time of 90 days.

Sponsor: SpineThera Australia Pty. Ltd

Protocol Number: CLIN-0012-STA01-19

SAP Version and Date: Amendment Final 1.1, 13JUL2022

4 DATA ANALYSIS CONSIDERATIONS

All analyses will be conducted based on SAS 9.4 or higher.

All data in the database will be presented in by-patient data listings.

Unless otherwise stated, all listings will be sorted by treatment group, center ID, patient number, and assessment date (and time, if available).

Unless stated otherwise, continuous data will be summarized by treatment group based on n, mean, median, standard deviation (SD), first quartile (Q1), third quartile (Q3), minimum value, and maximum value.

Unless stated otherwise, categorical data will be summarized by treatment group using n and percentage based on the number of non-missing values. The number of missing values will be presented as a separate category with no percentage, but only if one or more patients are missing data. Counts of zero will be presented without percentages.

The following levels of precision for reporting data will be applied:

- Mean, Median, Q1, and Q3: one additional decimal place to that reported for Minimum and Maximum
- SD: two additional decimal places than the Minimum and Maximum
- Percentages: reported to one decimal place

All data up to the time of study completion/withdrawal from the study will be included in the analysis, regardless of duration of treatment.

Numbering for data displays will be based on ICH E3⁽²⁾.

4.1 Stratification and Covariates

There are no formal plans for analysis stratification.

4.2 Evaluation of Subgroups

There are no formal plans for examining subgroups.

4.3 Multiple Comparisons and Multiplicity

No formal statistical hypothesis tests will be conducted.

5 GENERAL DATA HANDLING CONVENTIONS

5.1 Assigned and Actual Treatment

As described in Section 3.2, patients will be randomized to placebo or SX600 (low-dose or high-dose). The randomized treatment assignment will be used for listings as well as selected analyses indicated for the Intent-to-Treat population.

Sponsor: SpineThera Australia Pty. Ltd

Protocol Number: CLIN-0012-STA01-19

SAP Version and Date: Amendment Final 1.1, 13JUL2022

Actual treatment groups are based on exposure data to treatment received, and will be the basis for all safety analyses.

The following three treatment groups (actual or as-randomized) are planned in this study:

- Placebo
- SX600 at 12.5 mg DXA
- SX600 at 25.0 mg DXA

5.2 Reference Dates

The following reference definitions will be applied for this study:

- Screening date is defined as the eCRF provided date on which a patient was screened for trial entry.
- Day 0 is the date on which the patient is randomized to study treatment (i.e., Randomization date), and when TF-EI is performed (i.e., Intervention date).
- Treatment date is defined as the date of dose of study drug.
- The calculation of age will use the informed consent date as its reference date.
- Efficacy data will use the treatment date as a reference date.
- Study day will be based on treatment date as a reference date.

5.3 Definitions

The following definition will be applied for this study:

50% Responder: a patient with 50% or greater improvement in Mean Worst Daily Leg Pain score compared to baseline.

Mean Worst Daily Leg Pain score is based on the Numeric Rating Scale (NRS) as described in Section 7.1.

30% Responder: a patient with 30% or greater improvement in Mean Worst Daily Leg Pain score compared to baseline.

5.4 Study Day and Duration Variables

Reference date calculations will generally be defined as the following, assuming nonmissing dates:

- Date of interest – reference date.

If either date is missing, reference date calculations will not be performed. Date imputation will be performed as identified in Section 5.7.

For instance, study day will be based on the treatment date as the reference would either have a negative value if collected before dosing, zero if collect on the day of drug dosing, or a positive value if collected after the day of drug dosing.

Duration of time is dependent on reference dates and will be calculated in a manner similar to that of the reference date calculation, assuming that dates of interest will strictly follow reference dates

Sponsor: SpineThera Australia Pty. Ltd

Protocol Number: CLIN-0012-STA01-19

SAP Version and Date: Amendment Final 1.1, 13JUL2022

(e.g. no negative values). For example, duration on study is defined as the end of study date – screening date. Patients still participating in study follow up at the time of analysis will use imputed end of study dates as described in Section 5.7.

5.5 Study Time Periods

Safety reporting will be classified by the following study periods for analysis:

Pre-therapy is defined as the period prior to a patient's treatment date.

On-therapy is defined as the period between a patient's treatment date to the end of study, including the TF-EI procedure.

5.6 Baseline and Post-Baseline Changes

Unless stated otherwise, baseline and post-baseline change values will be based on the following:

For vital signs, mean worst daily leg pain, SF-36, and Oswestry disability Index, baseline will be the value collected on the Day 0 visit. For clinical laboratory tests and 12-lead ECG, baseline will be the last nonmissing value collected prior to or on the treatment date and time. Post-baseline values will be those collected after defined baseline date.

For Mean Worst Daily Leg Pain, baseline is defined as the calculated Mean Numeric Rating Scale (NRS) score of 5 days recorded using the patient electronic diary for the 10 days preceding the Day 0 visit. The calculation method for Mean Worst Daily Leg Pain is as described in Section 7.1.

Change from baseline is defined as: value – baseline value.

Percentage change from baseline is defined as: (value – baseline value)/baseline value X 100%.

Most extreme change: The maximum most extreme change will be based on the maximum post-baseline value; the minimum most extreme change will be based on the smallest post-baseline value. This calculation will consider all assessments collected during the on-therapy period, scheduled or unscheduled.

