22.2.3.4 Recovery Procedures Post- Epidural Injection

The patient should be transferred to the recovery area, where observations for at least 1 hour including intermittent pulse, respiration, blood pressure monitoring must be completed by a member of the study team.

Prior to discharge, a peripheral neurologic examination of the leg on the side of injection should be conducted by an approved Investigator to exclude any motor weakness, and confirmation of ability to walk and maintain secure balance should be confirmed.

Any complications attributable to, or following, the procedure should be promptly managed in an appropriate manner and recorded in the study documentation (CRF). Once the patient and the physician are satisfied that the patient has suffered no ill-effects, the patient can be discharged after a minimum of 1 hour of observation.

Discharge instructions include:

1. The patient is not to operate a motor vehicle or machinery for the remainder of the day of the procedure, because any numbness due to the local anaesthetic might interfere with their ability to use a pedal.
2. The patient should contact the physician who performed the procedure if they experience any unusual symptoms following the procedure including, but not limited to, headache, fever, chills, increased pain, or paralysis. Contact details must be provided to the patient at the time of discharge.
3. The patient should slowly resume previous activities over a period of several days.
4. Arrange for Visit 3 (14 days +/- 2 from dosing).
5. Instruction for continued daily recording each evening of Worst Daily Leg Pain in the electronic diary.
6. Remind the subject of the telephone call the next day, and again on Day 7 for safety assessment.

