22.2.3.6 Pharmacokinetic Sampling

Following IMP/placebo administration, subjects allocated to the Pharmacokinetic population, will remain in-patient for the scheduled venous blood collection over 24 hours for pharmacokinetic analysis.

After the pre-dose baseline blood sample, post-dose blood samples for the measurement of the dexamethasone concentration in systemic circulation will be collected at the following time-points post-dose: 30, 60, 90 minutes, 2, 4, 6, 8, 12, 20, and 24 hours. Subjects will be discharged from the Investigational Site following collection of the 24 hr PK sample and all 24-hour safety measures (as listed below for other subjects (Telephone call 1) have been conducted and recorded.

Pharmacokinetic sampling is further outlined in Attachment 03 Pharmacokinetic (PK) Laboratory Manual (CLIN-0038).

CLINICAL PROTOCOL

Sponsor: SpineThera Australia Pty Ltd

CLIN-0012-STA01-19 Revision: 06
Effective Date: 17 Jun2020

Page: 50 of 76

[REDACTED]

[REDACTED]

[REDACTED]

[REDACTED]

[REDACTED]

[REDACTED]

CLINICAL PROTOCOL

Sponsor: SpineThera Australia Pty Ltd

CLIN-0012-STA01-19 Revision: 06
Effective Date: 17 Jun2020

Page: 52 of 76

[REDACTED]

[REDACTED]

[REDACTED]

[REDACTED]

[REDACTED]

CLINICAL PROTOCOL

Sponsor: SpineThera Australia Pty Ltd

CLIN-0012-STA01-19 Revision: 06
Effective Date: 17 Jun2020

Page: 53 of 76

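### SAP 5.6 defines post-baseline by calendar date, so the named safety endpoint of vital-sign change to discharge cannot be derived for patients who go home on Day 0

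*SAP*

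**What the plan says.** The endpoint appears in the same words in SAP 2.2.1 and Protocol 20.3: "Changes from Baseline in clinical laboratory, urinalysis, vital signs, and ECG parameters to discharge and follow-up".

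SAP 5.6 gives the derivation. The baseline rule is: "For vital signs, mean worst daily leg pain, SF-36, and Oswestry disability Index, baseline will be the value collected on the Day 0 visit". The rule for later values is: "Post-baseline values will be those collected after defined baseline date". For the summary of extremes, "The maximum most extreme change will be based on the maximum post-baseline value", with a matching rule for the minimum. For laboratory tests and ECG, the same paragraph ties baseline to the date and time of treatment. The vital-sign sentence mentions neither the time of day nor the injection.

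SAP 5.2 makes Day 0 both the randomisation date and the injection date. SAP 5.5 starts the on-therapy period on the treatment date and includes the procedure in it. SAP 9.3.1 asks for vital-sign values and changes by visit and by time point, but lists no time points.

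For the period after the injection, Protocol 22.2.3.4 requires "observations for at least 1 hour including intermittent pulse, respiration, blood pressure monitoring must be completed by a member of the study team". It then says "the patient can be discharged after a minimum of 1 hour of observation". PK participants stay longer (Protocol 22.2.3.6): "Subjects will be discharged from the Investigational Site following collection of the 24 hr PK sample".

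**The concern.** The endpoint names discharge as a time point. For an outpatient, discharge falls on the day of the injection, which is the baseline date. A rule that admits only later dates removes that time point from the change-from-baseline analysis.

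Safety is a primary objective of this first-in-human trial. The recovery hour is when an acute effect of the injection on pulse or blood pressure would show. Under the rule as written, a programmer has no change to discharge to report for most patients and has reason to leave the recovery readings out of the most-extreme table. The reader of the study report would then see vital-sign changes from Day 14 onward and nothing for the hour after dosing, although the endpoint promises it.

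**Working it through.** This is a check of definitions. The plan gives no figure of its own to reproduce on this point.

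**Inputs**
- Vital-sign baseline: the Day 0 visit value, with no pre-injection limit (SAP 5.6).
- Post-baseline: collection date later than the baseline date (SAP 5.6).
- Day 0: the injection date (SAP 5.2).
- On-therapy: from the treatment date onward (SAP 5.5).
- Discharge, patients outside the PK subset: after at least 1 hour of observation (Protocol 22.2.3.4). That section also restricts driving "for the remainder of the day of the procedure" and arranges a telephone call for the next day, so discharge on Day 0 is the expected course.
- Discharge, PK subset: after the 24-hour sample (Protocol 22.2.3.6).
- Treated patients: 55. PK participants: 4 (SAP 3.1).

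**Step 1. Apply each rule to each kind of reading**

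| Reading | Date later than baseline date (SAP 5.6) | Later than injection time (proposed) | On-therapy (SAP 5.5) |
|---|---|---|---|
| Recovery or discharge, 1 hour after injection | No | Yes | Yes |
| PK discharge, 24 hours after injection | Yes | Yes | Yes |
| Day 14 visit | Yes | Yes | Yes |

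Only the first row changes with the rule, and for most patients that row is the discharge reading.

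**Step 2. Count the patients affected**

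- Discharged on the baseline date: 55 − 4 = 51; 51/55 = 92.7%.
- Able to have a discharge value that counts as post-baseline: at most 4; 4/55 = 7.3%.

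The 4 is an upper limit, because the readable text names no vital signs at 24 hours for PK participants. With a time-based rule, up to all 55 could contribute.

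**Step 3. Look for text that overrides the rule**

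- SAP 5.4 also works in whole dates: anything collected on the dosing day has study day zero.
- SAP 5.8 summarises by the visits identified in the CRF and does not separate readings before and after the injection.
- SAP 6.7 plans a listing of recovery procedures, not a summary of change.
- SAP 10 replaces the efficacy analyses with descriptive ones and does not withdraw this safety endpoint.

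None of these restores the Day 0 discharge change.

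**The case against.** The strongest reply is that a numeric discharge reading is not shown to exist in the database. Protocol 22.2.3.4 requires monitoring during recovery, but the only CRF entry it names is for complications. Protocol 23.5.4 describes the formal vital-sign assessment as a seated measurement at study visits. The study schedule table, the Visit 2 procedures, the eCRF and the mock shells are not available to read, and any of them could name a post-injection time point on Day 0. This stands. It makes the count of 51 an upper limit and the fix conditional. It does not reconcile the endpoint with the derivation rule.

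A second reply is that SAP 5.6 applies only by default and SAP 9.3.1 speaks of time points, so a programmer could tabulate a Day 0 post-injection change anyway. That is possible. But SAP 9.3.1 lists no time points, and no readable sentence tells the programmer to set the date rule aside.

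Two stronger inferences should be resisted. A reader might infer that a recovery reading could be taken as baseline, which would shift every later change in that patient. SAP 5.6 does leave the vital-sign baseline without an explicit pre-injection limit, but Protocol 19.2 calls for safety parameters, vital signs among them, to be collected before dosing. The documents therefore do not support saying that nothing prevents this. A reader might also infer that the most-extreme rule contradicts itself, since it uses post-baseline values yet takes in the whole on-therapy period. The two sentences can be read together, the second simply adding unscheduled assessments to the post-baseline pool. That leaves an ambiguity about Day 0 readings, not a contradiction.

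**Conclusion.** The point holds. As written, SAP 5.6 excludes a time point that SAP 2.2.1 and Protocol 20.3 name, for up to 51 of 55 treated patients (93%). The figure assumes that every patient outside the PK subset left on the injection date and that the 4 PK participants are among the 55 treated. It matters in practice only if recovery readings were recorded as numbers, which is likely but not shown. The exclusion of those readings from the most-extreme summary is arguable rather than certain.

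A reader might infer that acute safety information is lost. The documents do not support that. SAP 9.3.1 lists all vital signs, SAP 6.7 lists recovery procedures, complications go into the CRF, and an adverse event during or after the procedure on Day 0 counts as treatment-emergent under SAP 5.5 and 9.1. What is missing is the quantitative summary of acute vital-sign change. This is a wording error in the SAP with a small consequence, worth correcting because the correction is cheap.

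The point is limited to vital signs. No claim is made about a discharge ECG, because the readable text does not settle whether one was taken.

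**What to change.** - **SAP 5.6:** define the vital-sign baseline as the last reading before the injection on Day 0, and post-baseline as any reading after the injection time. Where clock times are missing, use the eCRF label (pre-dose or recovery).
- **SAP 9.3.1:** add one row for the last recovery reading before discharge on Day 0, with change from baseline by treatment received, and state that Day 0 post-injection readings enter the most-extreme summary.
- **If recovery readings were not captured as numeric data:** say so in SAP 10 and report the vital-sign endpoint for follow-up only.

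The cost is two sentences and one table row, with no new procedure or data collection. There is one drawback. Visit blood pressure is taken seated after at least 3 minutes (Protocol 23.5.4), and the readable text does not give the posture in recovery, so the discharge change may mix posture with treatment effect. A footnote to the new row should say so.
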